4.4 Biosafety: N/A

4.5 Stem Cells: N/A

4.6 Fetal Tissue: N/A

## 5.0 Procedures Involved

5.1 Study Design: prospective single blind placebo controlled n=1 study with 2 cross-overs

5.2 Study Procedures:

- NTproBNP on cilostazol and on placebo (see flow diagram) day 5 to 7 (5mL's) and day 25 to 28 (5 mL's) at any Fairview Lab site.
- Kansas City Heart Failure Questionnaire (KCCQ-12) will be administered by PI phone call day 7, 14, 21 and 28
- Baseline patient characteristics collected from Fairview EPIC

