## **15.0 Statistical Considerations**

*15.1* Data Analysis Plan:

Primary outcomes

**KCCQ heart failure questionnaire:** paired parametric test (t-test) of placebo average composite score and the cilostazol average composite score.

**NTproBNP:** Relative changes in NTproBNP level (placebo versus cilostazol) will be compared by paired parametric testing (t-test).

*15.2* Power Analysis:

In a recent large HFpEF clinical trial of sacubitril/valsartan the baseline KCCQ score was  $71 \pm 19$ . A sample size of 18 would provide us with 80% power to detect a 25% relative difference using a 2-sided test. We propose a sample size of 25 participants to ascertain 18 or greater completed studies. In a recently completed pacemaker study that leads to a similar increase in heart rate we found a beneficial outcome in a heart failure questionnaire in n=22 participants (see reference #4, Wahlberg et al.).

*15.3* Statistical Analysis:

Linear mixed-effect models determine the effect of cilostazol on the primary outcome, accounting for inter-patient differences and treatment assignment and sequences. For the primary endpoint, the KCCQ total score at the end of each week (week 1 to 4) is the dependent variable, while the treatment (cilostazol versus placebo) is the independent variable. Patient identifier and treatment sequence (binary variable marking the start of the treatment with placebo or cilostazol) are entered as random effects. The same approach was taken to assess the effect of cilostazol on NT-proBNP levels, after log-transforming NT-proBNP values given their skewed distribution. To determine the

treatment effect paired analyses of subsequent treatment periods will be performed (Wilcoxon test) to match weeks and the days within the treatment period.

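### The section 15.3 crossover models have no week or visit term, so a trend over the month goes into the error and, if the starting orders are unequal, into the treatment estimate

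*Combined protocol and SAP*

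**What the plan says.** Section 15.3 sets out a linear mixed model for the questionnaire in which "the KCCQ total score at the end of each week (week 1 to 4) is the dependent variable" and "the treatment (cilostazol versus placebo) is the independent variable". The other terms are random: "Patient identifier and treatment sequence (binary variable marking the start of the treatment with placebo or cilostazol) are entered as random effects". The same model form is applied to NTproBNP after log transformation. Neither 15.1 nor 15.3 contains a week, period or visit term.

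Section 15.3 adds a Wilcoxon analysis of successive periods, and 15.1 gives paired t-tests for both outcomes. None of these adjusts for time.

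KCCQ is taken on days 7, 14, 21 and 28. NTproBNP is drawn only twice (section 5.2): "day 5 to 7 (5mL's) and day 25 to 28 (5 mL's) at any Fairview Lab site".

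Section 4.1 gives one treatment order, starting on cilostazol. The binary sequence variable in 15.3 implies that some patients start on placebo. No randomisation method or allocation ratio is stated.

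**The concern.** In a crossover each treatment is observed at different times, so a patient's cilostazol-minus-placebo difference contains whatever changed between those times. Sequence is constant within a patient and cancels from that difference. Week does not cancel. The model therefore carries the order term that the contrast does not need and omits the time term that it does.

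A trend is plausible. The screening text in section 8.0 allows patients to be identified during a hospital admission, so their condition may change over the following month. NTproBNP is the more exposed outcome, because its two draws are about three weeks apart.

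Unequal groups are plausible too. No balancing is described, the plan allows for up to 25 - 18 = 7 non-completers, and section 12.2 stops data collection at withdrawal. At stake are the size of the estimated effect and the power to detect it.

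**Working it through.** **The plan's own figure.** Section 15.2 states: "A sample size of 18 would provide us with 80% power to detect a 25% relative difference using a 2-sided test". With mean 71 and SD 19, the difference is 0.25 × 71 = 17.75 points. Taking alpha as 0.05 (not stated), 2 × (1.960 + 0.842)² × 19² / 17.75² = 17.99, so 18. The figure reproduces (as the per-arm size of a two-group formula) and this point does not affect it.

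**Bias, KCCQ.** Let the score drift by b per week, so weeks 1-4 carry 0, b, 2b, 3b.
- Cilostazol first: (0 + 2b)/2 - (b + 3b)/2 = -b.
- Placebo first: +b.
- With n1 and n2 patients: bias = -b(n1 - n2)/(n1 + n2).

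This is 0 at 9:9, -0.11b at 10:8, -0.33b at 12:6 and -b at 18:0.

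**Bias, NTproBNP.** The draws fall in weeks 1 and 4, so each patient carries -3b or +3b. The bias is -0.33b at 10:8, -b at 12:6 and -3b at 18:0.

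**Chance of imbalance.** If order were decided by coin flip (assumed) among 18 completers, a split of 12:6 or worse has probability 0.238.

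**Does the random sequence term help?** No. In a mixed-model fit to simulated 12:6 data, the treatment estimate was -3.504 with patient and sequence random, identical to the within-patient estimate without sequence. With no true sequence effect, its variance would be estimated as zero about 67% of the time (P(F(1,16) < 1) = 0.668).

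**Error and type I error, KCCQ** (simulated, no true effect, 18 patients, assumed within-patient SD 9):

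| Split | Drift per week | Mean SE, no week term | Type I, no week term | Mean estimate, no week term | Mean estimate, week term |
|---|---|---|---|---|---|
| 9:9 | 0 | 2.11 | 5.2% | 0.01 | 0.01 |
| 9:9 | 2 | 2.19 | 4.7% | 0.00 | 0.00 |
| 9:9 | 4 | 2.44 | 3.0% | -0.09 | -0.09 |
| 12:6 | 4 | 2.43 | 5.6% | -1.35 | -0.03 |
| 18:0 | 2 | 2.18 | 13.0% | -1.97 | not estimable |
| 18:0 | 4 | 2.38 | 36.2% | -4.02 | not estimable |

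At 9:9 and 4 points per week, the week term brings the mean SE from 2.44 back to 2.11.

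**Power, KCCQ** (assumed weekly SD 8, effect 6 points), without and with the week term:
- 9:9, 1 point per week: 87% and 87%.
- 9:9, 2 points per week: 86% and 88%.
- 12:6, 4 points per week: about 55% and 83%. The expected estimate is 6 - 4/3 = 4.7.
- 12:6, no drift: 88% and 84%.

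**NTproBNP** (assumed log SD 0.25 per draw; the 25% fall in section 2.2 is ln 0.75 = -0.288):
- With coin-flip order and log drift between draws of 0 / 0.1 / 0.2 / 0.3, power is 91 / 88 / 81 / 69% without a visit term and 88% throughout with it.
- At 12:6 and drift 0.3, the expected estimate is -0.288 - 0.3/3 = -0.388, an exaggerated fall.
- At 6:12 and drift 0.3, it is -0.288 + 0.1 = -0.188, and power is 34% against 86% with the term.
- At 12:6 with no drift, the visit term takes power from 90% to 86%.

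**The case against.** The best case for the plan is that this is an exploratory study and the harm rests on assumed drift. Neither drift nor within-patient SD is in the documents. Four KCCQ points per week is 12 points from week 1 to week 4, twice the assumed effect, and a log drift of 0.3 exceeds the 25% fall the sponsor expects. With equal groups and modest drift, almost nothing is lost. That stands, and it limits the point to an inexpensive safeguard.

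Three stronger readings are tempting, and the documents do not support them.
- A reader might infer that the random sequence term distorts the result. It is uninformative with two levels, but it leaves the within-patient contrast unchanged.
- A reader might infer that any change over time biases the estimate. A step exactly between weeks 2 and 3 cancels from the KCCQ contrast at any split, though it still adds to the error.
- A reader might infer that false positives rise. When both orders were used, KCCQ type I error was near or below 5% at 9:9, 10:8 and 12:6. Clear inflation appeared in the one-order case. The result should not be stretched to much more lopsided splits, which approach that case, or to NTproBNP, which it did not cover.

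It may also be said that the Wilcoxon analysis matches weeks. Differencing successive weeks still leaves the week-to-week change in every difference.

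**Conclusion.** The point holds as an omission from the model. As written, section 15.3 leaves a monthly trend in the residual error and, with unequal starting orders, in the treatment estimate. The bias formulas are exact for linear drift and complete data. The power figures rest on 18 completers, 7-day periods, alpha 0.05 and the assumed SDs, effects and drifts. The loss runs from negligible (equal groups, 1-2 KCCQ points per week) to large (about 55% against 83% at 12:6 and 4 points per week). NTproBNP carries about three times the bias per week of drift.

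Where both orders are used, the harm shown is bias and lost power, and no excess of false positives was found for KCCQ up to a 12:6 split. Whether the full correction can be fitted depends on the disagreement between 4.1 and 15.3 about order. The sample size of 18 is not called into question here.

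**What to change.** First reconcile 4.1 with 15.3: state whether one or both starting orders are used and, if both, how patients are allocated to them.

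**If both orders are used,** amend 15.3 to:
- add week (1-4) as a fixed factor for KCCQ, and visit (first or second draw) as a fixed factor for log NTproBNP;
- enter sequence as a fixed effect or drop it, and keep patient random;
- name these models as the primary analysis, with the unadjusted paired t-tests in 15.1 and the Wilcoxon analysis as supporting only.

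**If only one order is used,** a categorical week factor is aliased with treatment. Only a linear week term can be fitted for KCCQ. For NTproBNP, visit and treatment coincide completely, so the report should say that the treatment effect cannot be separated from time.

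The change needs short edits to 4.1, 15.1 and 15.3. It uses 3 degrees of freedom for KCCQ and 1 for NTproBNP. If there is no drift it costs about 4 power points at a 12:6 split and almost none with equal groups. It should be written down before the data are seen, because a time term chosen afterwards would be open to challenge.

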#### 15.4 Data Integrity:

The de-identified data will be available to all key personnel to yield a fully transparent data analysis.

## 16.0 Health Information and Privacy Compliance

### 16.1 Select which of the following is applicable to your research:

- My research does not require access to individual health information and therefore assert HIPAA does not apply.
- I am requesting that all research participants sign a HIPCO approved HIPAA Disclosure Authorization to participate in the research (combined consent and HIPAA Authorization).
- I am requesting the IRB to approve a Waiver or an alteration of research participant authorization to participate in the research.

Appropriate Use for Research:

- An external IRB (e.g. Advarra) is reviewing and we are requesting use of the authorization language embedded in the template consent form in lieu of the U of M stand-alone HIPAA Authorization. Note: External IRB must be serving as the privacy board for this option.

### 16.2 Identify the source of Private Health Information you will be using for your research (Check all that apply)

- I will use the Informatics Consulting Services (ICS) available through CTSI (also referred to as the University's Information Exchange (IE) or data shelter) to pull records for me
- I will collect information directly from research participants.
- I will use University services to access and retrieve records from the Bone Marrow Transplant (BMPT) database, also known as the HSCT (Hematopoietic Stem Cell Transplant) database.
- I will pull records directly from EPIC.
- I will retrieve record directly from axiUm / MiPACS
- I will receive data from the Center for Medicare/Medicaid Services

I will receive a limited data set from another institution

Other. Describe:

16.3 Explain how you will ensure that only records of patients who have agreed to have their information used for research will be reviewed.

patients who do not agree to have their PHI assessed cannot be enrolled.

16.4 Approximate number of records required for review: 25

16.5 Please describe how you will communicate with research participants during the course of this research. Check all applicable boxes

This research involves record review only. There will be no communication with research participants.

Communication with research participants will take place in the course of treatment, through MyChart, or other similar forms of communication used with patients receiving treatment.

Communication with research participants will take place outside of treatment settings. If this box is selected, please describe the type of communication and how it will be received by participants.

16.6 Explain how the research team has legitimate access to patients/potential participants:

Subjects will have signed a consent including a HIPAA authorization.

Patients are from cardiology group where PI and Co-Investigators have legitimate access to these records.

16.7 Location(s) of storage, sharing and analysis of research data, including any links to research data (check all that apply).

In the data shelter of the [Information Exchange \(IE\)](#)

Store       Analyze       Share

In the Bone Marrow Transplant (BMT) database, also known as the HSCT (Hematopoietic Stem Cell Transplant) Database

Store       Analyze       Share

In REDCap (recap.ahc.umn.edu)

Store       Analyze       Share

In Qualtrics (qualtrics.umn.edu)

Store       Analyze       Share

MEDICAL PROTOCOL (HRP-590)

PROTOCOL TITLE: **Cilostazol for HFpEF**

VERSION DATE: 05.16.2020

In OnCore (oncore.umn.edu)

Store  Analyze  Share

In the University's Box Secure Storage (box.umn.edu)

Store  Analyze  Share

In an AHC-IS supported server. Provide folder path, location of server and IT Support Contact:

The path should be in the form of "\\vp.ahc.umn.edu\vp\Research\Study0004"  
HIPCO requires this information to verify the data are in a properly encrypted server.

Store  Analyze  Share

In an AHC-IS supported desktop or laptop.

Provide UMN device numbers of all devices:

**PI #20191597 = password protected PC in locked office PC (PI)  
encrypted Excel file**

Store  Analyze  Share

Other. Describe: N/A

Indicate if data will be collected, downloaded, accessed, shared or stored using a server, desktop, laptop, external drive or mobile device (including a tablet computer such as an iPad or a smartform (iPhone or Android devices) that you have not already identified in the preceding questions

I will use a server not previously listed to collect/download research data

I will use a desktop or laptop not previously listed

I will use an external hard drive or USB drive ("flash" or "thumb" drives) not previously listed

I will use a mobile device such as an tablet or smartphone not previously listed

16.8 Consultants. Vendors. Third Parties. N/A

16.9 Links to identifiable data: OnCore is the CTMS used to link patients to their study IDs. Information will be destroyed after the completion of the study in compliance with the University of Minnesota's documentation destruction policy (<https://policy.umn.edu/operations/recordretention-proc02>) and HIPAA law.

16.10 Sharing of Data with Research Team Members.  
UMN BOX and de-identified data via e-mail

*16.11* Storage and Disposal of Paper Documents: The information will be destroyed in accordance with the University of Minnesota's documentation destruction policy (<https://policy.umn.edu/operations/recordretention-proc02>). The department of Cardiology utilizes established contracts with shredding vendors.

## **17.0 Confidentiality**

*17.1* Data Security: De-identified data will be stored in UMN Box. Box Secure Storage is a secure environment delivered by the Center of Excellence for HIPAA Data intended for storing, sharing and accessing sensitive and private-highly restricted files.

Data and samples shared outside the institution: N/A

The consent documents and other documents may be in physical files housed in the PI's secured office. Subjects will be assigned a unique code, which will be included on the associated study data. Only trained members of the research team affiliated with this study will have access to the study information

## **18.0 Provisions to Monitor the Data to Ensure the Safety of Participants**

*18.1* Data Integrity Monitoring. Describe the following:

- The PI will personally oversee the progress of the study and to ensure that it is conducted, recorded, and reported in accordance with the protocol, standard operating procedures, and applicable regulatory requirements. Maintenance of, and the assurance of, data accuracy and consistency over its entire life-cycle will be monitored by the principle investigator and [name]. NTproBNP and heart failure scores data integrity will be assessed and verified by both investigators.
- CTSI monitoring service will be utilized to provide regular monitoring visits every 6 month or if there is any concern that data integrity is compromised to assure that the study is conducted, recorded, and reported in compliance with Good Clinical Practice. Monitoring is provided at no cost to PIs.

*18.2* Data Safety Monitoring.

There is no formal DSMB. AEs and UOPs will be reported to the clinical director of heart failure [name] MD. If she recommends a change in protocol this will be directly communicated to the IRB and enrollment will be halted until the changes are approved.

The data will be continuously monitored by the PI and shared in a de-identified file amongst key personnel.

## **19.0 Provisions to Protect the Privacy Interests of Participants**

### *19.1 Protecting Privacy:*

Only affiliated research team member will interact or obtain personal or sensitive information from study subjects.

We do anticipate any of the standard inquiries would make subjects feel uncomfortable; however, subjects do not have to answer questions that might make them feel uncomfortable.

### *19.2 Access to Participants:* Subjects will have signed the consent form including HIPAA allowing this access.

## **20.0 Compensation for Research-Related Injury**

### *20.1 Compensation for Research-Related Injury:* We will use the following UMN HRPP template language:

“In the event that this research activity results in an injury, treatment will be available, including first aid, emergency treatment and follow-up care as needed. Care for such injuries will be billed in the ordinary manner, to you or your insurance company. If you think that you have suffered a research related injury let the study physicians know right away.”

### *20.2 Contract Language:* N/A

## **21.0 Consent Process**

### *21.1 Consent Process (when consent will be obtained):* The consent process could take place: University of Minnesota Medical Center (UMMC), Clinics and Surgery Center (CSC) and Lillehei Clinical Research Unit (LCRU).

We will allow patients as much time as possible to consider participation in the study. A physician or care provider in the cardiology clinic or on the cardiology service will briefly tell the patient about the study and ask if they would like to discuss it further with a member of the research staff. If the patient agrees, a member of the study staff will meet with the patient and discuss the study in more detail. Potential subjects will come from the UMP Cardiology Clinic/Cardiology Inpatient/Outpatient service where PI and Co-Investigators clinically manage these patients.

Trained and affiliated members of the research team will determine that a potential participant understands the information during the consent process and discussion. Continued consent is assessed at each follow-up visit to ensure subject understanding and continued willingness to participate.

Documentation is comprised of a note in the subject file. The free text note outlines the consent process and discussion; any questions that arose and how the research team addressed those questions.

MEDICAL PROTOCOL (HRP-590)

PROTOCOL TITLE: **Cilostazol for HFpEF**

VERSION DATE: 05.16.2020

21.2 Waiver or Alteration of Consent Process (when consent will not be obtained): N/A

21.3 Waiver of Written/Signed Documentation of Consent (when written/signed consent will not be obtained): N/A

21.4 Non-English Speaking Participants: N/A

21.5 Participants Who Are Not Yet Adults (infants, children, teenagers under 18 years of age): N/A

21.6 Cognitively Impaired Adults, or adults with fluctuating or diminished capacity to consent: N/A

21.7 Adults Unable to Consent: N/A

- Permission: N/A
- Assent: N/A
- Dissent: N/A

## **22.0 Setting**

22.1 Research Sites: This information is already provided above in section 11 and 25 of this form; location information is provided in the ETHOS SmartForm.

22.2 International Research: N/A

## **23.0 Multi-Site Research**

N/A

## **24.0 Coordinating Center Research**

N/A

## **25.0 Resources Available**

25.1 Resources Available:

- Sample size is addressed above in section 15 above.
- We will take as much time as is required to safety and appropriately conduct the study in compliance with the approved B&I protocol.
- University of Minnesota Medical Center (UMMC), Clinics and Surgery Center (CSC), Fairview outpatient laboratories (any Fairview location), Lillehei Clinical Research Unit (LCRU)
- Affiliated research team is comprised of doctors and nurses with extensive clinical and research experience.
- Everyone obtaining consent has undergone IRB required research training. The PI and Co-PI are established researchers and clinicians with many years of experience in research. The study coordinators and research staff involved are experienced personnel who understand the tenets of good clinical practices.

